4.2 Exclusion Criteria

- 1. Unable to sign informed consent form.
- 2. Pregnant or breast-feeding females (lactating females must agree not to breast feed while taking the investigational agents).
- 3. Any condition, including the presence of laboratory abnormalities, which places the subject at unacceptable risk if he/she were to participate in the study or confounds the ability to interpret data from the study. For Example:
 - symptomatic congestive heart failure of New York Heart Association Class III or IV (Appendix 13.5)
 - unstable angina pectoris, symptomatic congestive heart failure, myocardial infarction within 6 months of start of study drug, serious uncontrolled cardiac arrhythmia or any other clinically significant cardiac disease
 - severely impaired lung function with O₂ saturation that is 88% or less at rest on room air
 - active (acute or chronic) or uncontrolled severe infections
 - condition requiring ongoing use of medications that are considered STRONG or MODERATE CYP3A4 inhibitors or inducers and P-gp substrates at study screening. However, those who require weak inhibitors/inducers can be enroll at discretion of the PI. See Appendix 13.2 for a list of excluded and cautionary concomitant medications.
 - liver disease such as cirrhosis or severe hepatic impairment (Child-Pugh class C).
- 4. Has a history (within the past 12 months) of (non-infectious) pneumonitis requiring systemic steroids, or active pneumonitis.
- 5. Bilirubin < 3 × ULN in the presence of liver metastases or presence of documented Gilbert's syndrome (unconjugated hyperbilirubinemia)
- 6. Concurrent use of other anti-cancer agents or therapies during study treatment.
- 7. Use of any other experimental drug or therapy within 28 days of initiating treatment with the investigational agents.
- 8. Known seropositive for or active viral infection with human immunodeficiency virus (HIV), hepatitis C (HCV), or hepatitis B virus (HBV); patients who are seropositive because of hepatitis B virus vaccine are eligible.
- 9. Previous use of JAK1 inhibitor (itacitinib), or history of progression on everolimus.

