4 STUDY POPULATION AND DURATION OF PARTICIPATION

4.1 Inclusion Criteria

- 1. Able to understand and voluntarily sign the informed consent form.
- 2. Aged 18 years or older at the time of signing the informed consent form.
- 3. Biopsy-proven diagnosis of relapsed classical Hodgkin lymphoma.
- 4. Measurable disease on imaging defined as at least one lesion that can be accurately measured in at least two dimensions by imaging (PET/CT, CT or MRI). Minimum measurement must be ≥ 15mm in the longest axis or ≥ 10mm in the short axis.
- 5. Relapsed or refractory disease (after at least 2 prior systemic therapies); patients must have relapsed after high-dose therapy with ASCT, or have been deemed ineligible for high-dose therapy with ASCT based upon the below criteria:
 - Patients that have either progressed after treatment with, be intolerant to, or are not a candidate for brentuximab and pembrolizumab or nivolumab. The reason for forgoing such therapies must be clearly documented.
 - Are not ASCT candidates due to chemo-resistant disease (unable to achieve CR or PR to salvage chemotherapy), advanced age (≥ 65 years of age), or any significant coexisting

Page 30 of 72

- medical condition (renal, pulmonary, or hepatic dysfunction) likely to have a negative impact on tolerability of ASCT
- 6. Disease free of other malignancies for greater than or equal to 2 years with the exception of basal cell, squamous cell carcinomas of the skin, fully excised melanoma in situ, carcinoma in situ of the cervix or breast.
- 7. Performance status of ECOG 0-2 (Appendix 13.3).
- 8. Laboratory test results within these ranges (of note, patients who have cytopenias due to documented cHL involvement of the bone marrow may be considered for enrollment after discussion with the PI, Medical Director and Sponsor):
 - Absolute neutrophil count (ANC) > 1,000/μL
 - Platelet count $> 75,000/\mu L$
 - Serum creatinine < 2.0 mg/dL
 - Bilirubin $< 2.0 \times ULN$ unless bilirubin increase was due to Gilbert's disease. Further evaluation should be performed to confirm and document the origin of increase.
 - AST and ALT $\leq 2.5 \times \text{institutional upper limit of normal (ULN)}$
 - Fasting cholesterol ≤ 300 mg/dL AND fasting triglycerides ≤ 300 mg/dL. NOTE: In case one or both of these thresholds are exceeded, the patient can only be included after initiation of appropriate lipid lowering medication prior initiating study treatment.

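### Exclusion criterion 5 bars patients with bilirubin below 3 × ULN, which contradicts inclusion criterion 8 and leaves values of 3 × ULN or more untouched

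*Combined protocol and SAP*

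**What the plan says.** Two numbered criteria in the protocol govern bilirubin at entry.

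- **Section 4.1, inclusion 8** requires bilirubin below 2.0 × ULN, "unless bilirubin increase was due to Gilbert's disease. Further evaluation should be performed to confirm and document the origin of increase". The exemption covers Gilbert's disease only. It has no upper limit, and there is no matching exemption for liver metastases.
- **Section 4.2, exclusion 5** reads "Bilirubin < 3 × ULN in the presence of liver metastases or presence of documented" Gilbert's syndrome. It sits under the heading "4.2 Exclusion Criteria", so meeting it keeps a patient out.

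The Study Summary carries the same item, with the same inequality sign, among its main exclusion criteria.

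**The concern.** An exclusion on a liver test would normally remove high values. This one removes values below a limit, including normal ones, in the two groups it names. Inclusion 8 points the other way: it admits low values and makes room for Gilbert's disease. If both are applied literally, patients whom inclusion 8 accepts are turned away by exclusion 5, and the only Gilbert's patients left are those with the highest values.

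Three things are at stake. The first is accrual: the trial plans 23 evaluable subjects at one centre, with 17 needed at the recommended Phase II dose, and the rule closes it to whole groups for no stated reason. The second is safety: Section 1.1 reports liver test elevations in about 50% of patients on itacitinib plus a PI3Kδ inhibitor (mostly grade 2 or lower, and attributed to that inhibitor), and Section 1.5 promises close monitoring of liver function. The chemistry row of Table 3 names only AST and ALT, so the eligibility criteria carry the only numeric bilirubin limits in the protocol, and they conflict. The third is conduct: enrolling an ordinary Gilbert's patient, or any patient with liver metastases but no Gilbert's syndrome, breaches exclusion 5. It would have to be handled as an exception or deviation under Section 8.6.

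**Working it through.** No sample size, power or error rate is involved. The check is a logical intersection of the two criteria.

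**Inputs**
- Inclusion 8 (Section 4.1) is met if bilirubin is < 2.0 × ULN, or if the increase is due to Gilbert's disease.
- Exclusion 5 (Section 4.2 and Study Summary) applies if bilirubin is < 3 × ULN and the patient has liver metastases or documented Gilbert's syndrome.
- A patient is eligible on bilirubin if inclusion 8 is met and exclusion 5 does not apply.

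For Gilbert's patients, any increase is assumed to be due to that condition.

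| Patient group | < 2 × ULN | 2 to < 3 × ULN | ≥ 3 × ULN |
|---|---|---|---|
| Neither condition | Eligible | Fails inclusion 8 | Fails inclusion 8 |
| Liver metastases, no Gilbert's | Meets inclusion 8, **barred by exclusion 5** | Fails inclusion 8 and barred by exclusion 5 | Fails inclusion 8 |
| Gilbert's, with or without liver metastases | Meets inclusion 8, **barred by exclusion 5** | Meets inclusion 8, **barred by exclusion 5** | **Eligible** |

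**Results**
- Liver metastases without Gilbert's: the patient must be < 2 × ULN and also not < 3 × ULN. No value satisfies both.
- Gilbert's: the exemption satisfies inclusion 8, so only exclusion 5 binds. Eligible values are ≥ 3 × ULN, with no ceiling.
- Exclusion 5 bars three cells that inclusion 8 admits, and bars no cell at ≥ 3 × ULN.

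**Other readings of item 5**
- *All documented Gilbert's syndrome is excluded, and the 3 × ULN limit belongs to liver metastases only.* The Gilbert's exemption in inclusion 8 then has no use, and patients with liver metastases remain barred below 3 × ULN.
- *The item was meant as an allowance up to 3 × ULN.* It is then under the wrong heading, and in liver metastases the band from 2 to < 3 × ULN conflicts with inclusion 8.
- *The inequality sign is reversed.* The contradiction goes, but for liver metastases without Gilbert's the item adds nothing, because inclusion 8 already stops at 2.0 × ULN.

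Each reading needs an edit, and they give different rules. The documents do not show which was intended.

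**The case against.** The strongest case on the other side is that this is an obvious slip. A sentence that excludes normal bilirubin is absurd on its face, staff would probably query it, and nothing shows an effect on the complete response endpoint, the two-stage design or the toxicity rules. With a single centre, there can be no divergence between sites. The gap at the top is also narrow: a patient with liver metastases, no Gilbert's syndrome and bilirubin of 3 × ULN or more still fails inclusion 8. The missing ceiling for Gilbert's comes from the open exemption in inclusion 8; exclusion 5 merely fails to supply one.

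There are other safeguards. Inclusion 8 requires the cause of the increase to be documented and caps AST and ALT at 2.5 × ULN. Exclusion 3 removes "Any condition, including the presence of laboratory abnormalities, which places the subject at unacceptable risk" and gives cirrhosis or severe hepatic impairment as an example.

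Much of this stands. The open upper end is confined to Gilbert's syndrome, the practical effect cannot be quantified, and the error is more likely one of drafting than of intent. It does not remove the contradiction. Exclusion 3 gives no bilirubin figure and works by judgement. It could keep a patient out, but it cannot let in someone whom exclusion 5 bars. Relying on staff to guess the meaning is also unsafe when the plausible readings lead to different decisions, notably for liver metastases between 2 and 3 × ULN.

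**Conclusion.** The concern holds. Exclusion 5 as written runs against inclusion 8. On bilirubin alone, it leaves no eligible value for liver metastases without Gilbert's syndrome, and it admits Gilbert's patients only at 3 × ULN or more. The sole route in for a patient with liver metastases is to have Gilbert's syndrome as well, with bilirubin at that level because of it.

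The conclusion rests on the literal text and on the Gilbert's exemption applying whenever the increase is due to that condition. The same sign in Section 4.2 and in the Study Summary makes a text-extraction error unlikely. The number of patients affected is not given and cannot be derived, because the documents report no frequency of liver metastases or Gilbert's syndrome in this population. No planned analysis changes. It must be corrected because it is an operative eligibility rule that gives the wrong result when followed.

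**What to change.** Reconcile the Study Summary exclusion list, Section 4.1 item 8 and Section 4.2 item 5, so that no patient is admitted by one criterion and barred by the other without that being intended. Either restate exclusion 5 to agree with inclusion 8, or delete it and put a single bilirubin rule in inclusion 8.

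The revised text should answer three questions, with the values set by the clinical lead:
1. What limit applies in liver metastases, including the band from 2 to < 3 × ULN?
2. What limit applies in Gilbert's syndrome, and does it have a ceiling?
3. Which rule governs when both are present?

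The cost is a short amendment to those places in the protocol. Sample size, decision rules and analyses are unaffected. If subjects are already enrolled, a check of screening bilirubin in those with either condition would show whether any entered against the current wording.

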4.3 Subject Recruitment

Subjects will be recruited from the clinical oncology practices at the Hospital of the University of Pennsylvania. Subjects will not be reimbursed for participation.

Itacitinib + everolimus in HL

Version 11.0 Page 32 of 72

4.4 Duration of Study Participation

From enrollment, subjects will remain on active treatment for up to two (2) years, or until progression, intolerance, withdrawal of the consent, or termination of the study. Additional cycles of investigational treatment may be added if in the opinion of the investigator that the benefit risk ratio for the subject continues to be favorable. Patients who, after starting this investigational combination therapy, lose the ability to obtain everolimus commercially and do not take it for duration of 28 days, will be taken off study. After end of treatment (EOT) visit, subjects will remain in follow-up for an additional two years.

4.5 Total Number of Subjects and Sites

The total planned number of evaluable subjects at UPenn will be 23 (including those in Phase I and II portions). To complete Phase I portion utilizing the 3 + 3 design, it is expected that 6 to 12 subjects will be enrolled. For phase II, 11 to 17 subjects will be enrolled. It is expected that total of 17-20 subjects will be treated at the RP2D dose since 3 to 6 patients from Phase I will be treated under the same regimen as Phase II patients. In order to be included in the tolerability review of Phase I, subjects must have received the cohort-specific dose of itacitinib and everolimus for at least 75% of the days during the first 28-day surveillance period or have experienced a DLT. Up to 5 additional subjects may be enrolled to achieve a minimum cohort size should withdrawal or dose interruptions/reductions result in subjects being non-evaluable during Phase I.

4.6 Vulnerable Populations

No vulnerable populations will be recruited.

4.7 Telemedicine Visits

To safeguard the welfare of subjects during COVID surges and/or situations that may negatively impact their safety, telemedicine visits may be utilized. The telemedicine option will be discussed with the subject prior to the scheduled visit. Visit documentation will state that the visit was conducted via telemedicine, and it will state which intervention(s) and/or assessment(s) were and were not completed. If clinically indicated, labs may be performed at an outside testing facility.

5 TREATMENT

5.1 Itacitinib

5.1.1 Description of Itacitinib

Refer to Section 1.2.1

5.1.2 Intervention Regimen

In Phase I, itacitinib tablets will be administered orally (PO) at the cohort-specific dose (Refer to Table 1/Figure 1) QD. In Phase II, itacitinib tablets will be administered PO at the RP2D identified in Phase I.

Page 33 of 72

Subjects may have dose reductions of itacitinib during the course of treatment based on AEs, clinical evaluation, and laboratory assessments. See Section 5.6.1 for itacitinib dose modification guidance.

Subjects are permitted to remain on itacitinib until withdrawal from study treatment is considered necessary or until 2 years of therapy. Additional cycles of investigational treatment may be added if in the opinion of the investigator that the benefit risk ratio for the subject continues to be favorable.

5.1.3 Receipt

Itacitinib will be provided to the study team as 100 mg tablets. All Incyte investigational product labels will be in the local language and will state "Caution: New Drug--Limited by Federal (or United States) law to investigational use."

5.1.4 Storage

All itacitinib drug product should be stored at ambient conditions (15°C to 30°C, or 59°F to 86°F).

5.1.5 Preparation

No preparation is required.

5.1.6 Administration and Accountability

Itacitinib may be taken without regard to food. Due to the potential for WBC margination, blood samples should be collected before study treatment administration at all applicable study visits.

The subject must be instructed in the handling of itacitinib as follows:

- Store the study medication at room temperature (15°C to 30°C, or 59°F to 86°F).
- Remove only the number of tablets from the study drug bottle needed at the time of administration.
- Do not remove doses in advance of the next scheduled administration.
- Make every effort to take doses on schedule.
- Report any missed doses.
- Take study medication with a glass of water.
- Do not take another dose if vomiting occurs after taking study medication.
- Do not take study medication on the day of clinic visits until after blood samples are collected.
- Keep study drug in a safe place and out of reach of children.
- Bring all used and unused study medication to the site at each visit.

Version 11.0 Page 34 of 72

5.2 Everolimus

5.2.1 Description of Everolimus

Refer to Section 1.2.2

5.2.2 Intervention Regimen

In Phase I and II, everolimus tablets will be administered orally (PO) at 5 mg QD.

5.2.3 Receipt

Everolimus will be acquired by the subject from a commercial pharmacy. The subject is prescribed 28 - 5 mg tablets, packaged in a carton (typically 4 individual blister cards each containing 7 tablets for a total of 28 tablets). However, if the pharmacy has to substitute the 5 mg strength (e.g., due to a shortage), the only substitution permitted is a 2.5 mg everolimus tablet. The subject should contact the clinic at the time the pharmacy informs them of the issue.

5.2.4 Storage

Everolimus tablets must be stored in accordance with storage conditions and shelf life as indicated in the manufacturer's approved label. Tablets are blister-packed under aluminum foil, which should be opened only at the time of administration as drug is both hygroscopic and light-sensitive.

5.2.5 Preparation

No preparation is required.

5.2.6 Administration and Accountability

Subjects will be instructed on how to handle their medication. Everolimus should be administered orally once daily, preferably in the morning, at the same time as the itacitinib every day with or without food. Everolimus tablets should be swallowed whole with a glass of water. The tablets must not be chewed or crushed.

The subject must be instructed in the handling of everolimus as follows:

- Store the study medication at room temperature.
- Remove only the number of tablets from the study drug blister pack as needed at the time of administration.
- Do not remove doses in advance of the next scheduled administration.
- Make every effort to take doses on schedule.
- Report any missed doses.
- Take study medication with a glass of water.
- Do not take another dose if vomiting occurs after taking study medication.

Page 35 of 72

- Do not take study medication on the day of clinic visits until after blood samples are collected.
- Keep study drug in a safe place and out of reach of children.
- Bring all used and unused study medication to the site at each visit.

5.3 Overdose

Any dose of itacitinib or everolimus in excess of that specified in this Protocol is considered to be an overdose. Signs and symptoms of an overdose that meet any SAE criterion must be reported as a SAE in the appropriate timeframe and documented as clinical sequelae to an overdose. Subjects who ingested more than the recommended dosage are instructed to immediately contact the study team and should be closely monitored and given appropriate supportive treatment.

5.4 Subject Compliance Monitoring

The subject compliance with the investigational regimen will be assessed during the scheduled visits via discussions with the subject and a count of the returned study drugs. Subjects will also be instructed to bring all study drugs with them to the study visits in order for site personnel to conduct tablet counts to assess study drug accountability. If subjects are determined to be non-compliant with the regimen, they may be removed from the trial at investigator discretion.

5.5 Return or Destruction of Investigational Product

Subjects will be asked to return all empty containers/blister packs and any unused study medication to each visit (see Sections 5.1.6 and 5.2.6). Unused itacitinib will be destroyed by the IDS pharmacy, when so authorized by the Sponsor. The everolimus is being dispensed through a specialty pharmacy contracted with the subject's insurance company. Study staff will adequately document pill counts and start/stop dates in the subject's EMR, but study staff will not collect or store unused everolimus that was supplied to a subject through their insurance company.

5.6 Modifications after DLT period

For subjects who are unable to tolerate the protocol-specified dosing schedule after DLT period (Cycle 1), dose adjustments are permitted in order to keep the subject on study drug for both itacitinib and everolimus. Treatment should also be delayed for major events (major events are non-treatment-related grade 3 and 4 hematologic and non-hematologic toxicities) if drug administration may further complicate the non-treatment related event. If a major event requires a delay of treatment, treatment must be delayed until toxicity is resolved (\leq Grade 1 or \leq baseline). For treatment-related toxicities and major events after the DLT period (for both phase I and II), if toxicity is not resolved in 4 weeks, subject will be permanently taken off study.

In a study using concurrent oral medications, it may be challenging to determine attribution especially since there may be some overlapping toxicities (e.g. cytopenias). Therefore, unless

Itacitinib + everolimus in HL
Version 11.0
Page 36 of 72

there is a clear attribution to one of the drugs, both drugs (itacitinib and everolimus) will be held or adjusted at the same time due to adverse events according to the guidelines below in Table 3.

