3.2 DLT Definition

A DLT will be defined as the occurrence of any toxicities in Table 2 occurring up to and including Day 28 of Cycle 1, except those with a clear alternative explanation (e.g., disease progression) or transient (≤ 72 hours) abnormal laboratory values without associated clinically significant signs or symptoms based on investigator and sponsor determination. All DLTs will be assessed by the investigator using CTCAE v5 criteria (NCI 2018). In order to be included in the tolerability review, subjects must have received the cohort-specific dose of itacitinib and everolimus for at least 75% of the days during the 28-day surveillance period of Cycle 1 or have experienced a DLT.

Individual subject dose reductions may be made based on events observed at any time during treatment with study drug (see Section 5.6); however, for the purposes of dose cohort escalation/de-escalation, expanding a dose cohort, and determining the RP2D, decisions will be made based on events that are observed from the first day of study drug administration through and including Day 28. A lower RP2D may subsequently be determined based on relevant toxicities that become evident after Day 28.

Subjects who experience a DLT or an unacceptable toxicity (i.e. not able to resume therapy within 28 days due to unresolved toxicity) beyond the DLT window will be also considered in the determination of the RP2D dose.

Any grade 5 hematologic and non-hematologic event related to the study treatments (at any time) will be considered a DLT.

Table 2: DLT defining toxicities

TOXICITY

Non-hematologic

- Any \geq Grade 3 non-hematologic toxicity, EXCEPT the following:
 - Transient (≤ 72 hours) abnormal laboratory values without associated clinically significant signs or symptoms.
 - Nausea, vomiting, and diarrhea adequately controlled with medical therapy within 48 hours.

Itacitinib + everolimus in HL
Version 11.0
Page 28 of 72

 Singular or non-fasting elevations in blood glucose (i.e., blood glucose excursions will be considered toxicities if fasting blood glucose is elevated on 2 separate sequential occasions).

Hematologic

- Grade 3 thrombocytopenia with bleeding.
- Grade 4 thrombocytopenia.
- Febrile neutropenia (ANC $< 1.0 \times 10^9$ /L and fever $> 101^\circ F/38.5^\circ C$).
- Grade 4 neutropenia that does not recover to \leq Grade 2 in \leq 3 days after interrupting study drug.
- Grade 4 anemia unresponsive to treatment for 3 days

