5.6.1 Dose Modification for Hematologic and Non-Hematologic Toxicities

Treatment with itacitinib and everolimus may be delayed up to 4 weeks (28 days) to allow for resolution of toxicity. Subjects may resume treatment if no medical condition or other circumstance exists that, in the opinion of the investigator, would make the subject unsuitable for further participation in the study. The treating investigator should contact the Sponsor Medical Director to discuss the case of any subject whose treatment has been delayed for more than 28 days before restarting treatment with itacitinib and everolimus.

Because subjects may enter the study with extensive pretreatment and/or severe bone marrow infiltration by the primary disease, dose interruption and reduction rules are provided as guidelines (see Table 3, Table 4, Table 5 and Table 6). Individual decisions regarding dose reduction following the DLT period should be made using clinical judgment, taking into account relatedness of the AE to the study drug and the subject's underlying condition. Adverse events that have a clear alternative explanation or transient (≤ 72 hours) abnormal laboratory values without associated clinically significant signs or symptoms may be exempt from dose-reduction rules.

Table 3: Guidelines for Interruption and Restarting Study Drugs due to AEs suspected to result from itacitinib or everolimus

ADVERSE EVENT		ACTION TAKEN			
CE	CHEMISTRY				
•	AST and/or ALT > 3.0 × ULN or > 3.0 of the baseline if baseline was abnormal	Step 1: Interrupt itacitinib and everolimus up to 28 days until the toxicity has resolved to \leq Grade 1 (unless approved otherwise by the medical director).			
		Step 2: Restart itacitinib and everolimus at same dose, if unrelated. If assessed as related to itacitinib, restart at next lower dose. If assessed as related to everolimus, restart at next lower dose. Monitor as clinically indicated.			
НЕ	HEMATOLOGY				
•	$ANC \le 1.0 \times 10^9/L$ unless due to underlying disease	Step 1: Interrupt itacitinib and everolimus up to 28 days until the toxicity has resolved to ≤ Grade 1 or pre-therapy baseline.			
•	Platelet count is $< 60 \times 10^9/L$ unless due to underlying disease	Step 2: Restart itacitinib and everolimus at same dose; monitor as clinically indicated.			
•	Grade 4 ANC (< 0.5 × 10 ⁹ /L)	Step 1: Interrupt itacitinib and everolimus up to 28 days until the toxicity has resolved to ≤ Grade 1.			

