8.7 Stopping Rules (safety and efficacy)

The safety analysis is based on Bayesian probability calculations and will be performed after the first 6 subjects treated at the RP2D and then after enrollment of 9, 12, and 15 subjects at RP2D dose. The maximum rate of unacceptable toxicity (AEs that would fit the definition of DLT from phase 1 at any point or AEs that do not allow the subject to restart treatment within 28 days) is 30% and a beta prior of (1,5) is assumed (that is 1 unacceptable toxicity in 6 subjects). The study will be terminated if 4 unacceptable toxicities in 6 subjects, 5 in 9, 6 in 12, or 7 in 15 are observed. The posterior probability that the true rate of unacceptable toxicities is above 30% at each stopping would be around 77 to 79% (79%, 78%, 78%, and 77%, respectively).

The efficacy analysis is based on Simon 2 stage optimal design and will be performed after the enrollment of the first 9 evaluable subjects treated at the RP2D. If there are no responders with CR from the first 9 evaluable subjects (at the 8 week or 16 week response assessment, at any itacitinib dose level), the null hypothesis (CR rate of 5% or lower with the new combination) will be considered as supported, and the study will be terminated. The study will be considered successful if the total number of subjects with CR is ≥ 2 in Phase II (at the 8 week or 16 week response assessment).

If there are two (2) study related deaths during the phase I portion of the trial, the study will be terminated.

Any death in the Phase II portion will result in pausing enrollment of the study until investigation is completed. If there are two (2) study related deaths in the Phase II portion of the study will be terminated.

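### For a toxicity still unresolved at 28 days, Section 5.6 requires permanent removal while Section 5.6.1 leaves restart possible

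*Combined protocol and SAP*

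**What the plan says.** Section 5.6 governs dosing after the DLT period. Its removal rule opens with its scope, "For treatment-related toxicities and major events after the DLT period (for both phase I and II", and ends with the outcome: "if toxicity is not resolved in 4 weeks, subject will be permanently taken off study". No exception is attached.

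Section 5.6.1, a subsection of 5.6, sets the limit on holding treatment: "Treatment with itacitinib and everolimus may be delayed up to 4 weeks (28 days) to allow for resolution of toxicity". It then deals with holds that pass the limit, by having the investigator consult the Sponsor Medical Director about "any subject whose treatment has been delayed for more than 28 days before restarting treatment with itacitinib and everolimus".

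The tables do not settle which governs:

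- Table 3, AST/ALT row: both drugs are interrupted for up to 28 days until Grade 1 or better, followed by the parenthesis "unless approved otherwise by the medical director".
- Table 3, other interruption rows: a hold of up to 28 days, with nothing on what follows if the toxicity has not resolved by then.
- Table 4, non-infectious pneumonitis, Grades 2 and 3: withdrawal from the study without recovery to Grade 1 or better within 28 days.

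The 28-day line also appears in two definitions used for decisions. Section 3.2 describes unacceptable toxicity as "not able to resume therapy within 28 days due to unresolved toxicity". The event counted by the safety stopping rule in Section 8.7 includes "AEs that do not allow the subject to restart treatment within 28 days".

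**The concern.** Two adjacent pieces of body text cover the same situation and do not give the same instruction. An investigator with a subject still in toxicity at day 28 can follow 5.6 and end participation, or follow 5.6.1, call the medical director, and possibly restart both drugs. Each course can be defended from the text.

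The choice decides whether the subject is re-exposed to a combination that has caused a lasting toxicity. It also fixes the off-treatment date and total exposure. Exposure bears on the chance of a later response, since Section 7.4 defines the Phase II primary endpoint by best overall response, although the documents give no basis for sizing that effect. If two subjects in the same position are handled differently, the difference reflects the paragraph that was read, not the plan.

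**Working it through.** The plan states no figure here, and the point rests on no sample size, power or event count. The check sets the texts side by side and works through two cases.

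**Inputs**

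- 5.6: trigger is toxicity not resolved in 4 weeks; outcome is permanent removal; scope is after Cycle 1, both phases.
- 5.6.1: delay for resolution of toxicity is limited to 4 weeks (28 days); trigger for the call is treatment delayed more than 28 days; outcome is a discussion before restarting.
- 3.2 and 8.7: the counted event is failure to resume within 28 days because of toxicity.

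**Same threshold?** 4 weeks × 7 days = 28 days. Both sections use the same limit.

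**Same trigger?** Not quite. Section 5.6 turns on the state of the toxicity, and 5.6.1 on the length of the delay. Two illustrative cases separate them:

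- *Case A: toxicity resolves on day 27, dosing could restart on day 30 for a reason other than toxicity.* Section 5.6 is not triggered, because the toxicity resolved inside 4 weeks. Section 5.6.1 is triggered, because the delay exceeds 28 days, and asks for a call. Both can be obeyed, so there is no conflict.
- *Case B: toxicity is still unresolved at day 28, restart is considered on day 30.* Section 5.6 requires permanent removal. Section 5.6.1 also applies and treats restart as possible after the call. Both cannot govern.

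**Is 5.6.1 confined to Case A?** Nothing says so. It opens by tying the delay to resolution of toxicity, and its call applies to any subject delayed beyond 28 days. Case B therefore falls inside it, and the conflict stands for that case.

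**Do the tables decide Case B?** The Grade 2 and 3 pneumonitis rows of Table 4 agree with 5.6, but only for that event. In the AST/ALT row of Table 3, the parenthesis directly follows the Grade 1 target. It may waive the grade, the 28 days or both, and the text does not say which. The remaining interruption rows are silent.

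**Does the toxicity count change?** In Case B the subject did not resume within 28 days and toxicity was the reason. That meets 3.2 and 8.7 whether the subject is then removed or restarts on day 30, because neither definition refers to what happens later. In Case A toxicity did not prevent resumption, so it is not counted whichever section is followed. The count is the same under either section.

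**The case against.** Four arguments can be made for the plan.

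- *The triggers differ, so the sections are compatible.* This is right for Case A. It does not help with toxicity unresolved at day 28, to which both sections apply.
- *Section 5.6.1 asks for a discussion and does not promise restart.* This stands and limits the point. A reader might infer that the sections prescribe opposite outcomes for any hold over 28 days, such as a 30-day hold. The documents do not support that: a 30-day hold whose toxicity resolved on day 27 is not removed by 5.6, and 5.6.1 guarantees no restart.
- *The rules are offered as guidelines, with clinical judgment.* Section 5.6.1 uses that term for the interruption and reduction rules in Tables 3 to 6. The removal sentence is body text in 5.6, worded as mandatory and permanent, and is not covered.
- *There is no statistical consequence for the safety decisions.* This stands. A reader might infer that the choice of section changes the toxicity count behind the RP2D or the stopping rule, for example moving a cohort from 1/6 to 2/6. The definitions in 3.2 and 8.7 count the subject either way, so no one is reclassified.

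A reader might also see a contradiction in Table 3, where the milder hematology row accepts Grade 1 or pre-therapy baseline and the more severe row accepts only Grade 1. These rows cover events of different severity with different restart actions, and 5.6.1 allows for marrow infiltration by calling the rules guidelines. A common recovery target would be a clinical preference, and none is asked for here.

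**Conclusion.** The point holds for one situation: a toxicity after Cycle 1, in either phase, that is still unresolved after 28 days. There the plan requires removal in one place and leaves restart open in another. It should be corrected because it decides whether a subject with unresolved toxicity may be re-exposed, and because it affects exposure and the off-treatment date.

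The size cannot be computed, since the frequency of holds reaching 28 days is not given. The nearest figures are in Section 1.4.2, from an earlier trial of everolimus: 53% of patients had dose reductions or treatment delays, and delays for thrombocytopenia were typically one week. Section 1.6 gives the dose in that setting as 10 mg daily against 5 mg here, so the figures do not transfer directly. It is an assumption, though a reasonable one, that few subjects would be affected.

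The conclusion assumes that 5.6.1 is read as written, without an unstated limit to subjects whose toxicity has already resolved. If that limit was intended, stating it would remove the conflict.

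**What to change.** The sponsor should reconcile Sections 5.6 and 5.6.1 so that one stated outcome applies to toxicity unresolved at 28 days. Three wording changes do this:

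1. Say which sentence governs when toxicity is unresolved at 28 days, and amend or delete the other.
2. State whether the discussion with the medical director in 5.6.1 applies only when toxicity has resolved but dosing has been delayed.
3. In the AST/ALT row of Table 3, say whether the medical-director exception covers the grade, the 28 days or both, and make it consistent with the rule chosen.

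Which clinical rule to adopt is for the sponsor; no view is taken here. Sections 3.2 and 8.7 need no change on this account. The cost is protocol wording only, with no effect on sample size or the planned analyses.
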